10.2 Patient Loss to Follow-up

In the event a patient cannot be reached for post-procedure assessments, at least three attempts will be made to contact the patient; efforts (and methods) to contact the patient will be documented. If the patient cannot be located and is determined to be unreachable, data collected up to the time of patient loss to follow-up will be submitted.

10.3 Early Termination or Suspension of the Clinical Study

Any decision to suspend enrollment or terminate the clinical study, either completely or at one or more clinical sites, will be made by the sponsor or the IRB. Reasons for early termination or suspension of a study (at one or more sites) may be due to ethical concerns, clinical site performance, or organizational issues. In the event of clinical site

or study closure, all patients who have received the study treatment will be followed until their primary endpoint is met.

The sponsor is responsible for reporting early termination or suspension of the study to the IRB(s) and principal investigators as required according to applicable regulations and standards.

11.0 Statistical Considerations

11.1 Sample Size

A sample size of 86 patients was determined using a confidence interval-based approach with the following assumptions:

- 80.1% success (freedom from hernia recurrence) at 1 year, based on recurrence rates for biologic meshes from literature review (Table 11.1-1).
- $\alpha = 0.05$, power = 0.8, margin = 10%
- 2-sided confidence interval

To account for patients lost to follow-up, this study intends to enroll 95 patients.

Table 11.1-1. Summary of Review Data on the Use of Biologic Graft for Ventral Hernia Repair

Paper	Mesh	Length of Follow up	Recurrence - pooled rate (n)	Infection Complications - pooled rate (n)
Clean/Clean Contaminated				
Darehzereshki A, et al., World J Surg. 2014	Biologic	14.7-66 mo	18.6% (311)	10.9% (155)
	Synthetic	13-66 mo	15.7% (533)	36.5% (85)
Lee L, et al., Surg Endosc. 2014	Biologic	Most > 1yr	12.5% (214)	31.6% (214)
	Synthetic	Most > 1yr	8.2% (434)	6.4% (434)
Fischer J et al., Plast Reconstr Surg. 2016	Biologic	12-32.9 mo	14.6% (159)	32.1% (159)
	Synthetic	12-39 mo	17.6% (135)	19.1% (135)
Clean Contaminated or Potentially Contaminated[#]				
Atema J et al., Am J Surg. 2016	Biologic	12-26.4 mo	9% (807)	21% (807)
	Synthetic	13.1-36 mo	9% (204)	12% (204)
Contaminated, Dirty or Infected				
Cross W et al., Am Surg. 2014	Biologic	5.8-52 mo	20% (554)	24% (554)
Lee L, et al., Surg Endosc. 2014	Biologic	Most > 1 yr	27.2% (549)	35.5% (582)
	Synthetic	Most > 1yr	3.2% (74)	42.6% (74)
Atema J et al., Am J Surg. 2016	Biologic	14-26 mo	30% (527)	38% (527)
	Synthetic*	10.8 mo	7% (100)	11% (100)
	Biologic	4.5 –29 mo	25.8% (357)	Not Provided

Hodgkinson J et al., Colorectal Dis. 2017	Synthetic	14 – 74 mo	29% (131)	Not Provided
--	-----------	------------	-----------	--------------

Atema et al. grouped clean contaminated and potentially contaminated cases together in the review paper

* Results from a single study (review was only able to identify one study on use of synthetics in contaminated fields)

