11.2 Analyses

Patients' baseline medical characteristics will be summarized. For continuous baseline characteristic variables, descriptive statistics will be provided; for categorical baseline characteristic variables, contingency tables will be tabulated to display the distribution.

The primary endpoint is the rate of hernia recurrence as defined in Appendix C through 1-year follow-up. Patients whose device is damaged in a subsequent procedure prior to reaching the primary efficacy endpoint will not be included in the primary endpoint analysis. The point estimate and the 95% confidence interval will be summarized.

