11.3 Hypothesis to be Tested

The primary hypothesis for effectiveness is the rate of hernia recurrence through 1-year follow-up (π_{graft}). The null (H_0) and alternative (H_A) hypotheses for the primary effectiveness are expressed as follows:

$$H_0 : \pi_{graft} \geq 22\%$$

$$H_A : \pi_{graft} < 22\%$$

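### The 80% power in Section 11.1 cannot be power for the 22% recurrence hypothesis in Section 11.3, which 86 patients test with about 6% power at the assumed 19.9%

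*Combined protocol and SAP*

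**What the plan says.** Section 11.1 (Sample Size) states: "A sample size of 86 patients was determined using a confidence interval-based approach". The inputs are "80.1% success (freedom from hernia recurrence) at 1 year", which is 19.9% recurrence; alpha 0.05 with "power = 0.8, margin = 10" (per cent); and a "2-sided confidence interval". Enrolment is raised to 95 for loss to follow-up. The section names no formula, does not say whether the 10% margin is absolute or relative, and does not mention 22%.

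Section 11.3 (Hypothesis to be Tested) begins "The primary hypothesis for effectiveness is the rate of hernia recurrence through 1-year follow-up" and sets the null as "H_0 : \pi_{graft} \geq 22" per cent, against an alternative below 22%. It gives no source for 22% and no separate design rate for the graft.

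Section 11.2 (Analyses) says of the primary endpoint: "The point estimate and the 95% confidence interval will be summarized". It gives no test statistic and no rule linking the interval to the hypothesis.

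**The concern.** Power, margin and hypothesis normally belong together: the margin is the distance between the assumed rate and the null value, and power is the chance of rejecting that null at the assumed rate. Here the stated margin is 10%, but the null lies 2.1 points from the assumed rate, and nothing in the documents connects the two sections.

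Two things are at stake. A reader who takes 0.8 as the power of the only stated hypothesis will expect a graft that performs as assumed to pass in four trials out of five, when it would pass in roughly one out of seventeen. And a failure to reject, the most likely result by far, could be taken as evidence that the device missed its target, when it would say almost nothing about that.

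**Working it through.** **Inputs.** From 11.1: n = 86, assumed recurrence p1 = 1 − 0.801 = 0.199, alpha 0.05, power 0.8, margin 10%, 2-sided interval. From 11.2: 95% interval. From 11.3: null p0 = 0.22.

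**Planning rate.** The n-weighted mean of the eight biologic rows in Table 11.1-1 is 69,077.4 / 3,478 = 19.86% recurrence. The 80.1% success figure is reproduced.

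**Can 86 be reproduced?**
- As a test of 19.9% against 29.9% (absolute 10-point margin), using n = (z_a·√(p0·q0) + z_b·√(p1·q1))² / (p0 − p1)²: 153 two-sided, 119 one-sided. The simpler n = (z_a + z_b)²·p1·q1 / (p0 − p1)² gives 126 and 99. None is 86.
- As precision: find the smallest n for which, at 80.1% success, the lower limit of a two-sided 95% Wilson interval lies within 10 points of the estimate with probability at least 0.8. The probability is 0.763 at n = 85 and 0.821 at n = 86, so this gives exactly 86. The match was found after trying several variants, so it shows a possible origin and no more.
- As a test of 19.9% against 22%: (1.960 × 0.4142 + 0.8416 × 0.3992)² / 0.021² = 1.3177 / 0.000441, about 2,990. One-sided 0.05 gives about 2,350. Neither is anywhere near 86.

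**Power against 22% with n = 86.** Reject when the upper limit of the two-sided 95% interval is below 22%.
- Exact upper limit: 21.7% at 11/86 and 23.1% at 12/86, so rejection needs 11 or fewer recurrences (12.8%). Wilson gives the same cut-off. The expected count at 19.9% is 86 × 0.199 = 17.1.
- P(X ≤ 11 | 86, 0.199) = 0.059.

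| Rule, n = 86 | Reject 22% at | Power at 19.9% |
|---|---|---|
| Two-sided 95%, exact or Wilson | ≤ 11 | 5.9% |
| Two-sided 95%, Wald | ≤ 12 | 10.3% |
| One-sided 0.05, exact or Wilson | ≤ 12 | 10.3% |
| One-sided 0.05, Wald | ≤ 13 | 16.5% |

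If all 95 enrolled patients are evaluable, the exact two-sided rule needs 12 or fewer and gives 4.4%; the fall comes from the discreteness of the exact cut-off.

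**Rate at which power reaches 80%.** With the cut-off of 11, P(X ≤ 11 | 86, p) is 0.802 at p = 0.106 and 0.794 at p = 0.107. True recurrence would have to be about 10.6% or lower, roughly half the planning rate.

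**Power against 29.9% with n = 86.** Exact or Wilson two-sided 95%: reject at ≤ 17, power 55%. One-sided 0.05, exact: reject at ≤ 18, power 65%. One-sided 0.05, Wald: about 75%. Read as a test at the absolute margin, the design does not reach 80% either.

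**The case against.** The strongest defence is that 86 was never meant to power a test. Section 11.1 describes a confidence-interval approach, in which a power of 0.8 can mean the probability of achieving a stated precision, and the Wilson calculation above lands on 86. This stands as a possibility. A reader might infer that the stated 80% is simply false, or that no calculation yields 86. The documents support neither: 11.1 never claims 80% for the test against 22%, and one precision criterion does reproduce the figure. But the defence leaves the gap in place, because the hypothesis in 11.3 then has no sizing behind it.

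A second defence is that 6% depends on the 19.9% rate. The four cleaner-field biologic rows of Table 11.1-1 average 12.1% (18,044 / 1,491), and at a true rate of 12.5% the exact power is 61%. That is correct, and the 6% should always be quoted with its condition. Still, 19.9% is the only design rate the plan gives, and even 61% is below 80%.

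A third is that the study is descriptive: its objective is to collect performance data, and 11.2 only summarises the estimate and interval. This limits the consequence. A reader might infer that the study will be reported as having failed its hypothesis, but the documents give no success rule and no consequence of not rejecting. Section 11.3 nevertheless sets out a primary hypothesis to be tested, so its power must be described correctly.

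Finally, a reader might infer that 22% came from a 10% relative margin, since 1.10 × 19.9% = 21.9%. The documents do not say so. Even if true, the distance is still 2.1 points and 86 patients remain far too few.

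**Conclusion.** The mismatch between 11.1 and 11.3 holds on the plan's own figures, and no other section reconciles it. At a true recurrence of 19.9%, 86 evaluable patients give about 6% power against 22% with a two-sided 95% exact or Wilson interval, and about 10% to 16% under the one-sided or Wald alternatives. No usual choice of interval or sidedness comes near 80%, so the 0.8 in 11.1 cannot be power for the stated hypothesis. What it does represent is open: assurance of precision is plausible but undocumented, and as power against 29.9% it is not attained. The result assumes independent binomial outcomes, 86 evaluable patients and the plan's own planning rate.

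**What to change.** Reconcile the two sections before results are seen, leaving enrolment unchanged.

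**Section 11.1.** Name the formula, say whether the 10% margin is absolute or relative, and define the 0.8. If it is assurance, relabel it as the probability of achieving the precision target and present 86 as a precision-based size, with an illustration: 17/86 (19.8%) gives an exact 95% interval of 12.0% to 29.8%. If it was meant as power for the 11.3 hypothesis, delete it.

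**Section 11.3.** Give the basis for 22%. State that the test has about 6% power at 19.9%, so that failure to reject is not read as evidence that the device missed its target. Make the estimate with its exact or Wilson 95% interval the basis for the conclusion, and state the decision rule for the test, for example that the null is rejected if the upper limit of that interval is below 22%.

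Change the 22% threshold only if a documented rationale shows that another value was originally intended. Raising it to 29.9% to suit the sample size would make the primary hypothesis easier to meet and would still give only about 55% power.

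**Cost.** Text changes in two sections and no additional patients. The downside is that the stated power becomes less favourable.

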11.2 Analyses

Patients' baseline medical characteristics will be summarized. For continuous baseline characteristic variables, descriptive statistics will be provided; for categorical baseline characteristic variables, contingency tables will be tabulated to display the distribution.

The primary endpoint is the rate of hernia recurrence as defined in Appendix C through 1-year follow-up. Patients whose device is damaged in a subsequent procedure prior to reaching the primary efficacy endpoint will not be included in the primary endpoint analysis. The point estimate and the 95% confidence interval will be summarized.

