7.5.3 Rationale for Endpoints

The endpoints and measures were chosen since hernia recurrence and adverse events related to the use of surgical grafts have been identified as issues of clinical interest; many of these events often result in additional surgical procedures. Furthermore, patient quality of life has been chosen as an additional measure to capture the outcome of the intervention from the patient's perspective. Using patient-reported outcomes measures, we will be able to evaluate abdominal wall function and patient's perception of pain independently of hernia recurrence.

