9.2 Point of Enrollment

Patients are considered enrolled in the study when the device implant procedure is completed.

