10.0 Participation Endpoints of the Study

A patient's participation in the study will end after any of the following:

- Completion of all scheduled clinical evaluations through 2 years
- Subsequent procedure due to recurrence of the original hernia defect
- Any subsequent surgical procedure resulting in removal of the study device
- Patient withdrawal
- Principal investigator withdrawal of patient
- Patient loss to follow-up
- Patient death

After a patient exits the study for any reason, there are no study-specific requirements for follow-up and no additional data will be collected. Any data collected up to the point of patient exit may be used in the study.

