11.4 Planned Subgroups and Covariates

All patients enrolled in the study, except patients whose device is damaged in a subsequent procedure prior to reaching the primary efficacy endpoint, will be included for the primary analyses. If warranted, baseline characteristics (including but not limited to: patient demographics and hernia type) and procedural details (including but not limited to: procedure type (laparoscopic or open), surgical repair technique, fascial closure, and location of device placement) will be analyzed to determine their impact on the hernia recurrence rate.

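### Sections 11.2 and 11.4 drop implanted patients whose graft is later damaged: a possibly outcome-related exclusion with an ambiguous trigger and no all-implanted analysis

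*Combined protocol and SAP*

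**What the plan says.** The endpoint is set in section 11.2: "The primary endpoint is the rate of hernia recurrence as defined in Appendix C through 1-year follow-up". The same section then restricts who contributes to it: "Patients whose device is damaged in a subsequent procedure prior to reaching the primary efficacy endpoint will not be included" in the primary endpoint analysis. Section 11.4 uses the same restriction to describe the primary population: "All patients enrolled in the study, except patients whose device is damaged in a subsequent procedure prior to reaching the primary efficacy endpoint, will be" taken into the primary analyses.

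Four other places bear on the rule:

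- Section 9.2 fixes the point of enrolment: "Patients are considered enrolled in the study when the device implant procedure is completed". Anyone caught by the rule is therefore already enrolled and implanted.
- Section 7.5.3, explaining why recurrence and graft-related adverse events were chosen, says that "many of these events often result in additional surgical procedures".
- Section 10.0 ends participation after a repeat procedure for recurrence, and also after "Any subsequent surgical procedure resulting in removal of the study device". It allows data gathered before exit to be used. Damage without removal is not listed as a reason for exit.
- Section 11.5 plans per-protocol and analyzable populations without defining either. Its three approaches to missing data are written for missing physical exams.

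Appendix C does not define damage to the device. The rule makes no distinction by the reason for the later procedure.

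**The concern.** The study has one arm, so the primary result is a single proportion. Its meaning depends on who is in the denominator. Here, membership depends on an event after implantation that the plan itself associates with the outcomes being measured. If the patients removed have a different recurrence risk from those kept, the estimate no longer describes everyone who received the graft, and the comparison with 22% in section 11.3 loses its nominal error rate.

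Three features make this more than a theoretical worry:

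- The trigger can be read in two ways, and one reading deletes known recurrences.
- Damage is undefined, so whether a patient counts may be decided case by case after the outcome is known.
- No specified analysis puts these patients back, so a reader of the results could not see what the rule had done.

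**Working it through.** **1. What the trigger means.** The rule applies to "except patients whose device is damaged in a subsequent procedure prior to reaching the primary efficacy endpoint".

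- *Event reading* (the endpoint is reached when a recurrence occurs). A recurrence documented before the later procedure stays in the numerator. A recurrence first discovered at the damaging procedure is exposed to deletion. Appendix C does not clearly cover an asymptomatic finding made during surgery without imaging.
- *Time-point reading* (the endpoint is reached at the 1-year assessment). A recurrence repaired at month 6 with damage to the graft is removed from numerator and denominator.

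Section 10.3 speaks of following patients until the primary endpoint is met. A recurrence-free patient could never meet an endpoint that is the event, so this usage leaves the time-point reading open. The text does not settle the matter.

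**2. The planned numbers.** Section 11.1 gives 86 evaluable patients, 80.1% success, α = 0.05, power 0.8 and margin 10%. No formula is named. The 86 is reproduced as the first n at which the lower limit of a two-sided 95% Wilson interval lies within 10 points of the estimate with probability at least 0.8: 0.763 at n = 85 and 0.821 at n = 86. Enrolment is 86 × 1.10 = 94.6, rounded to 95. The spare 95 − 86 = 9 patients are justified by loss to follow-up (11.1) and withdrawal (11.5), not by this exclusion.

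**3. Effect on the estimate.** Expected recurrences are (1 − 0.801) × 86 = 17.1, taken as 17. Exclude k patients, of whom j had recurred or would have recurred. The estimate becomes (17 − j)/(86 − k). The values of k and j are assumptions. Intervals are exact (Clopper-Pearson) 95%.

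| k excluded | j recurrent | Estimate | 95% CI |
|---|---|---|---|
| 0 | 0 | 17/86 = 19.8% | 12.0–29.8% |
| 4 | 4 | 13/82 = 15.9% | 8.7–25.6% |
| 4 | 2 | 15/82 = 18.3% | 10.6–28.4% |
| 4 | 0 | 17/82 = 20.7% | 12.6–31.1% |
| 8 | 8 | 9/78 = 11.5% | 5.4–20.8% |
| 8 | 0 | 17/78 = 21.8% | 13.2–32.6% |

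If 4 patients with no recurrence were instead kept and counted as failures, the result would be 21/86 = 24.4% (15.8–34.9%).

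**4. Effect on the test.** Let the true rate among all implanted patients be 22%, the boundary of the null in section 11.3. Exclude 5% of 86 (4.3), leaving 82 analysed. If the excluded patients have recurrence risk r, the rate among those kept is (0.22 − 0.05r)/0.95. The plan names no test; an exact one-sided 0.025 test is assumed, to match the two-sided 95% interval. It rejects at 10 or fewer recurrences out of 82.

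| r | Rate among kept | Probability of false rejection |
|---|---|---|
| 22% | 22.0% | 0.017 |
| 50% | 20.5% | 0.036 |
| 100% | 17.9% | 0.111 |

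At r = 22% the exclusion is uninformative and the test stays below 0.025. At r = 50% it exceeds that level, and at r = 100% it is more than four times it.

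**The case against.** A reader might infer that the rule preferentially removes recurrent cases and so necessarily flatters the device. The documents do not support that. On the event reading, recurrences documented before the procedure are kept, and section 10.0 permits use of data up to exit. Unrelated abdominal surgery also triggers the rule, and there is an arguable, though unstated, reason for not charging the graft with damage done in such surgery. If the excluded patients had not recurred, the estimate rises.

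A reader might also take the infection rates for biologic grafts in Table 11.1-1 (10.9% to 38%) as a sign that many patients would be excluded. Those are infection complications, not re-operations and not graft damage. The documents give no rate for either.

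Nor do small exclusions overturn the test in the illustration. From 17/86 the upper limit is 29.8%, and with 4 recurrent patients removed it is still 25.6%. Even if every excluded patient had recurred, it is 22.05% at 7 excluded (10/79) and first falls below 22% at 8 (9/78, 20.8%).

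Finally, simply censoring these patients would assume that censoring is unrelated to recurrence, which is the assumption in doubt.

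All of this stands, and it limits the claim about direction and size. It does not answer the remaining problem: the primary population depends on a post-implant event that can be related to outcome, through an ambiguous rule, with no analysis that restores the patients removed.

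**Conclusion.** The point holds as a potential bias of uncertain direction. On the time-point reading, or when recurrence is first found at the damaging procedure, true recurrences are deleted and the rate is biased downward. When the excluded patients had not recurred, it is biased upward.

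For an assumed 4 exclusions, the estimate moves from 19.8% to somewhere between 15.9% and 20.7%. For scale, the planned 19.9% lies 2.1 points below the 22% threshold. The false-rejection probability at a true 22% ranges from 0.017 to 0.111 when 5% are excluded, depending on their risk. These figures rest on assumed counts, assumed recurrence shares and an assumed exact test. They show what the rule could do, not what it will do, and do not show that the study's conclusion would change. The defect in the wording rests on none of these assumptions.

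**What to change.** Replace the exclusion in sections 11.2 and 11.4 as follows, before outcome data are examined:

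1. Include all implanted patients in the primary analysis.
2. Count as an event any recurrence documented before the later procedure or found at it, and say how a finding made during surgery is classified under Appendix C.
3. If no recurrence is found, treat follow-up as ending at that procedure, for example with a 1-year Kaplan-Meier estimate and its 95% CI. Section 11.2 does not currently plan a time-to-event estimate, so state the day at which it is read; the 1-year window in section 9.4 runs from 275 to 455 days.
4. Because that censoring may be informative, add a sensitivity analysis counting damage or removal in a hernia-, device- or wound-related procedure as failure.
5. Report the exclusion analysis now in the plan as secondary. Define damage, and state whether reaching the endpoint means the event or the 1-year assessment.

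The cost is revised wording, one or two extra tables, and possibly a less favourable recurrence rate. No additional patients or visits are needed.

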11.3 Hypothesis to be Tested

The primary hypothesis for effectiveness is the rate of hernia recurrence through 1-year follow-up (π_{graft}). The null (H_0) and alternative (H_A) hypotheses for the primary effectiveness are expressed as follows:

$$H_0 : \pi_{graft} \geq 22\%$$

$$H_A : \pi_{graft} < 22\%$$

